#### Standard of care:

VLU standard of care treatment will be performed according to local practice requirements but reapplied at least every third day until complete epithelization. Standard of care will include the following:

1. Wound bed preparation, i.e.:
  - Careful wound cleansing with water, saline, Ringer's solution or preserved mechanical wound cleansers (i.e. polyhexanide (Prontosan, Lavanid), or hypochlorous (Granudacyn, Microdacyn) irrigation)
  - Wound debridement if necessary and as per standard of care (e.g. mechanical or surgical debridement)
2. Application of appropriate breathable wound dressing which must be selected among the following categories and with regard to routine local care, level of exudate, and healing stage:
  - Hydrofiber: Exufiber, Aquacel Extra
  - Foam dressings: Mepilex XT, Mepilex Lite, Biatain Soft Hold, Biatain Silicone lite, Aquacel Foam, UrgoTul Lite
  - Wound Contact layer: Mepitel, Mepitel One, Adaptic Touch, UrgoTul
  - Superabsorbant: Mextra, Kiliniderm Superabsorber, Zetuvit Plus/Resposorb
3. Application of appropriate compression therapy which must be selected among the following categories and with regard to routine local care, level of exudate, and healing stage:
  - Multilayer compression: [REDACTED]
  - Hosiery and stockings compression: [REDACTED]  
[REDACTED]

NB: Dressings including active components are not allowed. Within a clinic, there must be consistency in the choice in dressings, i.e. the same sequence of dressings should be kept for all the patients.

3. Application of appropriate compression therapy which must be selected among the following categories and with regard to routine local care, level of exudate, and healing stage:

- Multilayer compression: [REDACTED]
- Hosiery and stockings compression: [REDACTED]  
[REDACTED]

- Short stretch bandages

NB: A multilayer compression system is preferred and consistency in compression therapy throughout the study is mandatory, unless patient compliance issues necessitate change. Patients must be withdrawn from study in case of severe non-compliance to compression therapy.

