In between clinical visits, wound management will follow standard of care. Home visits will be performed by study nurses who are responsible for changing dressing, reapplying Granulox® (for patients randomized to the treatment group only), and reapplying compression therapy. See details in Section 3.5.1.1. Home visits frequency will follow local practice requirements but must take place at least every 3rd day until epithelization is complete. The study nurse will record information in the patient-specific diary. If considered necessary, nurses can ask for an additional patient visit to the investigating centre. This is mandatory at suspected complete wound closure.

If at any time, a wound graft is required (it usually requires at 24-48 hours hospitalization), study will not be considered as completed and patients will still be followed according to the schedule of assessments (even if experimental treatment is no longer applied) up to CCC occurrence or up to W20 (whichever occurs first).

[figure not shown]
The study will be stopped before W20 for a given patient in the event of:

- Consent withdrawal
- Impossibility to follow the patient (i.e. lost to follow-up)

- Hospitalization of more than 48h for any reason other than wound graft
- Death
- Reach of endpoint and study completion, i.e. CCC.

In any other cases, including the cessation of experimental treatment for any reason, patient will continue study visits as per schedule of assessment. See details on analyses sets in Section 5.2.1.

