### 3.3.2.1 Confirmed Complete wound Closure (CCC)

CCC is the primary variable and main efficacy criterion. It is defined as an blinded assessment and observation of 100% re-epithelialization, confirmed by a second visit 15 days later (+/- 3 days). If a wound graft is required, patients will be followed to observation of CCC.

Blinded quantification of each wound picture will be made using PictZar® Digital Planimetry Software.

CCC will be derived from two measurements of 100% re-epithelialization by PictZar®, 15 days (+/- 3 days) apart.

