### **3.4.4 Withdrawal of Subjects from Treatment or Assessment**

Subjects are free to discontinue participation in the study at any time, and without prejudice to further treatment. Subjects who withdraw from the study should always be asked about the reason(s) for their discontinuation and about the presence of any Adverse Event/Adverse Device Effect or Device Deficiency and, if possible, be assessed by the Principal Investigator. Each reported Adverse Event/Adverse Device Effect will be followed up.

Subjects may be withdrawn from the study at any time, at the discretion of the Principal Investigator.

Incorrectly enrolled or randomised subjects will be withdrawn from the study. A subject may, however, continue study involvement under special circumstances (i.e. if continuation of study-related treatment or follow-up actions are necessary for the subject's safety and well-being, or if only a follow-up period remains, and the continuation of the subject's study involvement is not expected to be associated with any risk or discomfort for the subject).

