### **5.2.2 General statistical methodology**

This study will use confirmative and explorative analyses. All confirmative analyses will be based on FAS. Confirmative analysis of primary variables will also be performed based on PP.

Imputing of missing data in outcome variables will generally be used. For confirmative analyses, multiple imputations with Fully Conditional Specification (FCS) will be used for primary efficacy analysis. Confirmative secondary analysis and exploratory analyses will use stochastic imputation with FCS. Missing data on demography and background variables will not be replaced.

The study include testing analysis of the primary variable and sequential testing of selected secondary variables for confirmative analysis.

The study utilized stratified randomization based on site, wound size, and wound duration. This is reflected by a stratified primary analysis adjusted for these variables. For adjusted comparison between the two randomized groups, multivariable logistic regression will be used for dichotomous variables and analysis of covariance for continuous variables.

Continuous variable will be described with mean, SD, median, minimum and maximum and categorical variables with numbers and percentages. For unadjusted and adjusted analyses, mean differences with 95% CI will be calculated. For dichotomous variables, for descriptive purpose, relative risk with 95% CI will also be calculated. All significance analyses will be two-sided and conducted at the 5% significance level.

For unadjusted comparison between the two randomized groups Fisher's exact test will be used for dichotomous variables, Fisher's non-parametric permutation test for continuous variables, Mantel-Haenszel chi-square test for ordered categorical variables, and Chi-Square test for non-ordered categorical variables.

Applicable descriptive statistics and non-parametric statistical test methods are used to describe and explore secondary variables. For explorative analyses, no multiple-test considerations are made. For time to endpoint outcomes the Kaplan-Meier model and logrank test are used unadjusted and Cox proportional hazard model for adjusted analyses.

[figure not shown]

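### Outcome collection stops after any non-graft hospital stay over 48 h, creating avoidable missing closure data, and the closed stop list conflicts with the withdrawal rules elsewhere in the protocol

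*Protocol*

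**What the plan says.** **Stop list.** Protocol 3.2 lists five events that end a patient's study before week 20: consent withdrawal, loss to follow-up, "Hospitalization of more than 48h for any reason other than wound graft", death, and reaching CCC. It then closes the list: "In any other cases, including the cessation of experimental treatment for any reason, patient will continue study visits as per schedule of assessment". SAP 1.2.1 repeats both.

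**Grafted patients.** The same section treats a graft differently: "patients will still be followed according to the schedule of assessments (even if experimental treatment is no longer applied) up to CCC occurrence", or to week 20 if that comes first.

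**Withdrawals not on the list.**
- The synopsis, under standard of care, and again Protocol 3.5.1.1: "Patients must be withdrawn from study in case of severe non-compliance to compression therapy".
- Protocol 3.4.4: "Subjects may be withdrawn from the study at any time, at the discretion of the Principal Investigator".
- Protocol 3.4.4: "Incorrectly enrolled or randomised subjects will be withdrawn from the study". An exception lets such a subject stay in special circumstances, for example where only follow-up remains.

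**Endpoint and analysis.** Protocol 3.3.2.1: "CCC will be derived from two measurements of 100% re-epithelialization by PictZar®, 15 days (+/- 3 days) apart". The primary analysis is logistic regression on the full analysis set (FAS), and Protocol 5.2.2 says that "multiple imputations with Fully Conditional Specification (FCS) will be used for primary efficacy analysis". The one sensitivity analysis visible in Protocol 5.2.2.1 is an unadjusted Fisher's exact test with no imputation. SAP 3.2, on missing data, is visible only as a heading.

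**The concern.** CCC needs two full-closure readings about 15 days apart. A patient whose study stops in between, or before the first reading, cannot supply them. A stay over 48 h for any non-graft reason therefore ends collection of the primary outcome for a living patient who may still consent and could still be photographed. The protocol already accepts outcome follow-up off experimental treatment after a graft, so the loss comes from the stop rule and is not a practical necessity.

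These stops occur after randomisation in an open-label trial. If they differ by arm, and if stopped patients heal at a different rate from those who are followed, the imputed comparison moves. A withdrawal made at the investigator's discretion is also made with the allocation known.

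The conflict between sections is separate. A site that withdraws a patient for severe compression non-compliance follows the synopsis and 3.5.1.1 but breaks 3.2. A site that keeps the patient does the reverse. The choice decides whether a primary outcome is collected, and sites may choose differently.

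**Working it through.** **1. Stop list against the other sections**

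| Event | Protocol 3.2 / SAP 1.2.1 | Elsewhere in the protocol |
|---|---|---|
| Wound graft | Follow-up continues | No conflict seen |
| Non-graft stay over 48 h | Study stops | No conflict seen |
| Severe compression non-compliance | Not listed, so visits continue | Mandatory withdrawal (synopsis; 3.5.1.1) |
| Investigator discretion | Not listed, so visits continue | Withdrawal allowed at any time (3.4.4) |
| Incorrect enrolment or randomisation | Not listed, so visits continue | Withdrawal, with an exception (3.4.4) |

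Because 3.2 assigns every unlisted case to continued visits, the last three rows are contradictions and not mere gaps.

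**2. What happens to a stopped patient's CCC**

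A patient with at least one ordinary follow-up visit is in the FAS (Protocol 5.2.1). Without two readings, CCC can be derived as No or treated as missing and imputed. The visible text does not choose. SAP 3.1 mentions multiple imputation at week 20 for drop-outs, but within the final-visit definition and after a sentence on secondary variables, so it does not settle the matter for CCC. The Fisher test does not say whether stopped patients are dropped or counted as not closed.

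**3. Illustration of size**

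There is no plan figure to reproduce: stop rates are not given and the sample-size inputs are blacked out.

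Inputs:
- N = 254 (Protocol 3.1); 1:1 allocation is assumed, so n = 254/2 = 127 per arm.
- Assumed closure among patients followed: p = 0.55 (Granulox) and 0.40 (control).
- Assumed imputation on arm and baseline only, so the imputed rate in an arm equals p.
- d is the share stopped and q is true closure among those stopped.

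True rate in an arm = p(1 − d) + qd. One stopped patient therefore shifts that arm's imputed rate by (p − q)/n.

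| q | Granulox patient | Control patient |
|---|---|---|
| 0 | 0.55/127 = +0.43 points | 0.40/127 = −0.31 points |
| 0.2 | 0.35/127 = +0.28 points | 0.20/127 = −0.16 points |
| q = p | 0 | 0 |

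Signs show the effect on the difference, Granulox minus control. With q = 0, three Granulox and one control patient stopped give (3 × 0.55 − 0.40)/127 = +0.98 points. None against three gives −(3 × 0.40)/127 = −0.94 points.

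In terms of stop shares, the imputed difference is 15.0 points throughout. The true difference would be:

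| Stopped, Granulox v control | q = 0 | q = 0.2 | q = p |
|---|---|---|---|
| 2% v 1% | 14.3 | 14.5 | 15.0 |
| 6% v 4% | 13.3 | 13.7 | 15.0 |
| 10% v 5% | 11.5 | 12.5 | 15.0 |
| 5% v 10% | 16.25 | 15.25 | 15.0 |

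For example, 10% v 5% at q = 0 is 0.55 × 0.90 − 0.40 × 0.95 = 0.495 − 0.380 = 11.5 points.

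With true closure of 40% in both arms and q = 0, the normal approximation gives two-sided rejection of 5.05%, 5.22% and 6.51% for the first three rows, and 5.0% when stopping is equal.

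**The case against.** The strongest reply is that the missing-data rules belong in SAP 3.2, whose text is not shown. Withheld text is not absent text. Protocol 5.2.2 says only that imputation of outcomes will generally be used, which leaves room for exceptions. The CCC definition can itself be read as making an unhealed death a non-closure with nothing to impute. All of this stands, so the handling of deaths is a point to confirm.

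Second, the illustration may overstate the shift. Final-visit assessments are due at premature arrest (Protocol 3.3.8). If that wound area enters the imputation model, a patient with a large open ulcer would seldom be drawn as closed. The stop rule covers stays for any reason, and no section links those stays to poor healing, so q = p and zero shift are possible. Patients with planned hospitalisation are ineligible, and those with no ordinary follow-up visit are outside the FAS and are not imputed. This also stands and keeps the weight low.

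Third, SAP 3.3 reports withdrawal reasons by arm. That would reveal an imbalance but not how far it moves the result.

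None of this answers the two visible points: the stop rule discards outcomes that could be collected, and the withdrawal statements contradict the closed list.

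**Conclusion.** Two things hold on visible text. Protocol 3.2 and SAP 1.2.1 end primary-outcome collection after a non-graft stay over 48 h although grafted patients are still followed, which creates avoidable missing CCC data. The closed stop list also contradicts the synopsis, 3.5.1.1 and 3.4.4.

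A reader might infer that the plan will impute patients who died unhealed as closed, or that it favours Granulox. The documents do not support either reading. The rule may sit in SAP 3.2, and the direction of any shift depends on which arm has more stops and how those patients heal.

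The magnitude cannot be derived from the documents. Under the stated assumptions the shift per stopped patient runs from zero (q = p) to 0.43 points for Granulox or 0.31 for control (q = 0), in opposite directions. It is small unless stops are frequent and unequal. Priority is low, but the remedy is cheap.

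**What to change.** 1. **Long stays.** For consenting patients, continue outcome assessment only after a stay over 48 h: the scheduled photographs and the confirming one. Care does not change. Cost: wording in the protocol and SAP, and a few extra visits and photographs.
2. **Withdrawals.** Reconcile the synopsis, Protocol 3.5.1.1 and 3.4.4 with Protocol 3.2 and SAP 1.2.1, and state whether outcome photographs continue for withdrawn patients. This review does not say which withdrawal rule is right. Cost: wording only.
3. **Sensitivity analysis.** Unless SAP 3.2 already has one, add a non-closure or tipping-point analysis by arm, and state how stopped patients count in the Fisher test. Cost: one or two analyses. A non-closure analysis will count as failures some stopped patients who later closed.
4. **Confirm in SAP 3.2.** Check that death before confirmed closure counts as CCC = No, and that post-baseline wound area, including the reading at premature arrest, enters the imputation model. If both are already there, nothing changes.

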### 3.2.1 Flow Chart

NB. Wound management as per standard of care, at least every 3rd day until complete epithelialization, will take place between visits D0-W20. Extra clinical visits between visits D0-W20 are allowed and should be issued in the event of suspected wound closure.

### 3.3 *Efficacy and Safety*

### 3.3.1 Subject Characteristics

Demography and background data with potential impact on wound healing will be collected at the initial visit, i.e. :

- Date of birth
- Gender
- Ethnicity
- Mobility
- Vital signs (e.g. height/weight)
- Social profile (e.g. autonomy, lifestyle, social support)
- Relevant medical history (general and with regard to venous disease/VLU)
- Relevant surgical history (general and with regard to venous disease/VLU)
- Current wound management treatment
- Current wound status

### 3.3.2 Primary Efficacy Measurement and Variable

Digital photographs, taken after wound bed preparation at each clinical visit, will be used as a basis for the primary and secondary efficacy measurements and variables.

### 3.3.2.1 Confirmed Complete wound Closure (CCC)

CCC is the primary variable and main efficacy criterion. It is defined as an blinded assessment and observation of 100% re-epithelialization, confirmed by a second visit 15 days later (+/- 3 days). If a wound graft is required, patients will be followed to observation of CCC.

Blinded quantification of each wound picture will be made using PictZar® Digital Planimetry Software.

CCC will be derived from two measurements of 100% re-epithelialization by PictZar®, 15 days (+/- 3 days) apart.

### 3.3.3 Secondary Efficacy Measurements and Variables

Term	Panel 1 (%)	Panel 2 (%)	Panel 3 (%)
GMOs	~50	~50	~50
Organic	~95	~90	~95
Natural	~90	~95	~90
Artificial	~50	~50	~95

Investigation Code Granulox01 Final Version Approval date 2019-10-24

A horizontal bar chart illustrating the distribution of 1000 data points across 10 bins. The x-axis represents the value of the data points, and the y-axis represents the frequency or density of the bins. The distribution is highly right-skewed, with the highest frequency in the first bin (0-10) and a long tail extending to the right. The bins are labeled as follows:

- Bin 0: 0-10 (Frequency: 100)
- Bin 1: 10-20 (Frequency: 90)
- Bin 2: 20-30 (Frequency: 80)
- Bin 3: 30-40 (Frequency: 70)
- Bin 4: 40-50 (Frequency: 60)
- Bin 5: 50-60 (Frequency: 50)
- Bin 6: 60-70 (Frequency: 40)
- Bin 7: 70-80 (Frequency: 30)
- Bin 8: 80-90 (Frequency: 20)
- Bin 9: 90-100 (Frequency: 10)
- Bin 10: 100-110 (Frequency: 5)
- Bin 11: 110-120 (Frequency: 2)
- Bin 12: 120-130 (Frequency: 1)
- Bin 13: 130-140 (Frequency: 1)
- Bin 14: 140-150 (Frequency: 1)
- Bin 15: 150-160 (Frequency: 1)
- Bin 16: 160-170 (Frequency: 1)
- Bin 17: 170-180 (Frequency: 1)
- Bin 18: 180-190 (Frequency: 1)
- Bin 19: 190-200 (Frequency: 1)
- Bin 20: 200-210 (Frequency: 1)
- Bin 21: 210-220 (Frequency: 1)
- Bin 22: 220-230 (Frequency: 1)
- Bin 23: 230-240 (Frequency: 1)
- Bin 24: 240-250 (Frequency: 1)
- Bin 25: 250-260 (Frequency: 1)
- Bin 26: 260-270 (Frequency: 1)
- Bin 27: 270-280 (Frequency: 1)
- Bin 28: 280-290 (Frequency: 1)
- Bin 29: 290-300 (Frequency: 1)
- Bin 30: 300-310 (Frequency: 1)
- Bin 31: 310-320 (Frequency: 1)
- Bin 32: 320-330 (Frequency: 1)
- Bin 33: 330-340 (Frequency: 1)
- Bin 34: 340-350 (Frequency: 1)
- Bin 35: 350-360 (Frequency: 1)
- Bin 36: 360-370 (Frequency: 1)
- Bin 37: 370-380 (Frequency: 1)
- Bin 38: 380-390 (Frequency: 1)
- Bin 39: 390-400 (Frequency: 1)
- Bin 40: 400-410 (Frequency: 1)
- Bin 41: 410-420 (Frequency: 1)
- Bin 42: 420-430 (Frequency: 1)
- Bin 43: 430-440 (Frequency: 1)
- Bin 44: 440-450 (Frequency: 1)
- Bin 45: 450-460 (Frequency: 1)
- Bin 46: 460-470 (Frequency: 1)
- Bin 47: 470-480 (Frequency: 1)
- Bin 48: 480-490 (Frequency: 1)
- Bin 49: 490-500 (Frequency: 1)
- Bin 50: 500-510 (Frequency: 1)
- Bin 51: 510-520 (Frequency: 1)
- Bin 52: 520-530 (Frequency: 1)
- Bin 53: 530-540 (Frequency: 1)
- Bin 54: 540-550 (Frequency: 1)
- Bin 55: 550-560 (Frequency: 1)
- Bin 56: 560-570 (Frequency: 1)
- Bin 57: 570-580 (Frequency: 1)
- Bin 58: 580-590 (Frequency: 1)
- Bin 59: 590-600 (Frequency: 1)
- Bin 60: 600-610 (Frequency: 1)
- Bin 61: 610-620 (Frequency: 1)
- Bin 62: 620-630 (Frequency: 1)
- Bin 63: 630-640 (Frequency: 1)
- Bin 64: 640-650 (Frequency: 1)
- Bin 65: 650-660 (Frequency: 1)
- Bin 66: 660-670 (Frequency: 1)
- Bin 67: 670-680 (Frequency: 1)
- Bin 68: 680-690 (Frequency: 1)
- Bin 69: 690-700 (Frequency: 1)
- Bin 70: 700-710 (Frequency: 1)
- Bin 71: 710-720 (Frequency: 1)
- Bin 72: 720-730 (Frequency: 1)
- Bin 73: 730-740 (Frequency: 1)
- Bin 74: 740-750 (Frequency: 1)
- Bin 75: 750-760 (Frequency: 1)
- Bin 76: 760-770 (Frequency: 1)
- Bin 77: 770-780 (Frequency: 1)
- Bin 78: 780-790 (Frequency: 1)
- Bin 79: 790-800 (Frequency: 1)
- Bin 80: 800-810 (Frequency: 1)
- Bin 81: 810-820 (Frequency: 1)
- Bin 82: 820-830 (Frequency: 1)
- Bin 83: 830-840 (Frequency: 1)
- Bin 84: 840-850 (Frequency: 1)
- Bin 85: 850-860 (Frequency: 1)
- Bin 86: 860-870 (Frequency: 1)
- Bin 87: 870-880 (Frequency: 1)
- Bin 88: 880-890 (Frequency: 1)
- Bin 89: 890-900 (Frequency: 1)
- Bin 90: 900-910 (Frequency: 1)
- Bin 91: 910-920 (Frequency: 1)
- Bin 92: 920-930 (Frequency: 1)
- Bin 93: 930-940 (Frequency: 1)
- Bin 94: 940-950 (Frequency: 1)
- Bin 95: 950-960 (Frequency: 1)
- Bin 96: 960-970 (Frequency: 1)
- Bin 97: 970-980 (Frequency: 1)
- Bin 98: 980-990 (Frequency: 1)
- Bin 99: 990-1000 (Frequency: 1)

Investigation Code Granulox01 Final Version Approval date 2019-10-24

### 3.3.7 Safety Measurements and Variables

Adverse Events (AE) and Serious Adverse Events (SAE) will be collected in the study to measure safety associated to study treatments from ICF signature until study completion.

The definition of AE, Adverse Device Effect (ADE), SAE, Serious Adverse Device Effect (SADE), and Device Deficiencies (DD) and procedures for reporting SAE and SADE and DD that could have led to a SADE are presented in section 11 of this CIP. All AE, ADE, SAE, SADE and DD must also be recorded in the appropriate section of the CRF. It is of utmost importance that all staff involved in the clinical investigation is familiar with the content of section 11. It is the responsibility of the Principal Investigator to ensure this.

**Investigation Code** **Granulox01** **Final Version** **Approval date** **2019-10-24**

### 3.3.8 Schedule of Assessment

Site visits	Run-in Visit	Home care	Visit 1	Home care	Visit 2	Home care	Visit 3	Home care	Visit 4	Home care	Visit 5	Home care	Visit 6	Home care	Visit 7	Final Visit a)	Extra visit
Time frames	D-14	D-14-D0	D0 (At least every 3 rd day)	W1 (Day 7 ±1 day)	At least every 3 rd day	W4 (Day 28 ±3 days)	At least every 3 rd day	W8 (Day 56 ±3 days)	At least every 3 rd day	W12 (Day 84 ±3 days)	At least every 3 rd day	W16 (Day 112 ±3 days)	At least every 3 rd day	W20 (Day 140 ±3 days)			
Informed consent	X																
Eligibility criteria	X		X														
Randomization			X														
Demography and background data			X														
Medical and surgical history (including VLU)			X														
Wound picture	X		X		X		X		X		X		X		X	X	
PictZar®	X		X		X		X		X		X		X		X	X	
			X		X		X		X		X		X		X	X	
			X		X		X		X		X		X		X		
			X		X		X		X		X		X		X	X	
			X		X		X		X		X		X		X		
			X		X		X		X		X		X		X		
			X		X		X		X		X		X		X		
			X		X		X		X		X		X		X		
			X		X		X		X		X		X		X		
			X		X		X		X		X		X		X		
			X		X		X		X		X		X		X		
Adverse events e)			X		X		X		X		X		X		X	X	
Medications	X		X		X		X		X		X		X		X	X	

